5.5.1. Definitions

5.5.1.1. Clinical Endpoints

5.5.1.1.1. Modified Mayo Response

Modified Mayo response is defined as a decrease from baseline in modified Mayo score $\geq 30\%$ and ≥ 2 points, with either a decrease in the RBS ≥ 1 or a RBS of 0 or 1.

5.5.1.1.2. Symptomatic remission

Symptomatic remission is defined as a stool frequency subscore of 0 or 1, where the stool frequency subscore has not increased from baseline, and a rectal bleeding subscore of 0.

5.5.1.1.3. Endoscopic healing

Endoscopic healing (i.e., improvement in the endoscopic appearance of the mucosa) is defined as an endoscopy subscore of 0 or 1 with no friability present on the endoscopy.

5.5.1.1.4. Endoscopic normalization (i.e. normalization of endoscopic appearance of mucosa in protocol)

Endoscopic normalization is defined as an endoscopic subscore of 0 with no friability present on the endoscopy.

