3.2.3. Other Efficacy Endpoints

Combination Comparison Phase (ie, through Week 12)

- Endoscopic healing at Week 12 (Mayo endoscopic subscore of 0 or 1).
- Normalization of endoscopic appearance of the mucosa (Mayo endoscopic subscore of 0).
- Histologic healing at Week 12.
- Mucosal healing at Week 12 (Composite Mayo endoscopic healing and histologic healing).
- Change from baseline in the total score of the Inflammatory Bowel Disease Questionnaire (IBDQ) at Weeks 6 and 12.
- A >20 -point improvement in the IBDQ score at Weeks 6 and 12.
- Change from baseline in the 7 domains and the abdominal pain numerical rating scale of Patient-Reported Outcomes Measurement Information System (PROMIS)-29 at Weeks 6 and 12.
- Fatigue response at Weeks 6 and 12 (based on the PROMIS Fatigue Short Form 7a; to be defined in the SAP).
- Clinical response, clinical remission, and endoscopic healing at Week 12 by negative response signature status at baseline.
- Change from baseline in the Mayo score at Week 12.

- Change from baseline in the partial Mayo score through Week 12.
- Change from baseline in CRP through Week 12.
- Change from baseline in fecal calprotectin concentration through Week 12.
- Normalization of CRP concentration at Week 12 among participants with abnormal CRP concentration at baseline.
- Normalization of fecal calprotectin concentration at Week 12 among participants with abnormal fecal calprotectin concentration at baseline.
- Ulcerative Colitis Endoscopic Index of Severity (UCEIS) score at Weeks 0 and 12 by the level of Mayo endoscopy score at the corresponding visit.
- Change from baseline in the UCEIS score at Week 12.
- UCEIS score ≤ 4 at Week 12.
- UC-related emergency department visits, hospitalizations, and surgeries through Week 12.

Monotherapy Phase (ie, after Week 12)

- Clinical remission at Week 38.
- Clinical response at Week 38.
- Maintenance of clinical response at Week 38 among participants who achieved clinical response at Week 12.
- Endoscopic healing at Week 38.
- Normalization of endoscopic appearance of the mucosa at Week 38.
- Histologic healing at Week 38.
- Mucosal healing at Week 38.
- Clinical remission and not receiving concomitant corticosteroids at Week 38.
- Maintenance of clinical remission at Week 38 among participants who achieved clinical remission at Week 12.
- Change from baseline in the total score of the IBDQ at Weeks 24 and 38.
- A >20-point improvement in the IBDQ score at Weeks 24 and 38.

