The Mayo stool frequency subscore is calculated as follows: The absolute stool number is the average of the daily stool number over the three days. At the screening visit, each person indicates the number of stools he/she passed in a 24-hour period when in remission or before his/her UC diagnosis. The stool frequency subscore will be calculated based on the criteria in Attachment 1 by subtracting the number of stools when in remission or prior to UC from the absolute stool number.

Instructions on which 3 days to use in the calculation of the Mayo rectal bleeding and stool frequency subscores: Sites are directed to use the most recent 3 consecutive days within the 7 days prior to the visit and are directed to exclude the following:

- The day medications were taken for constipation, diarrhea or irregularity
- The day of a procedure or preparation for procedure (e.g. enema, other laxatives, or clear liquid diet) that would affect stool frequency and/or blood content of the stool
- The 48 hours after the use of antimotility agents (e.g. diphenoxylate hydrochloride with atropine sulfate or loperamide)
- The 48 hours immediately following a colonoscopy

If 3 consecutive days are not available, the sites are instructed to choose 2 consecutive days and the closest nonconsecutive day. If 2 consecutive days are not available, then 3 nonconsecutive days closest to the visit should be chosen. If 3 days (within the 7 days prior to the indicated visit) that meet the criteria defined above are not available, then the absolute stool number, stool frequency subscore, and rectal bleeding subscore cannot be calculated and will be missing in the eCRF.

Mayo Endoscopy Subscore

The endoscopic findings will be based on the criteria of the Mayo endoscopy subscore described in Attachment 1. The endoscopic findings will be assessed by the investigator (ie, local endoscopist) during the endoscopy procedure and by the central reader reviewing a video of the endoscopy. The endoscopy may be either a colonoscopy or sigmoidoscopy. A full colonoscopy will replace a sigmoidoscopy if screening for polyps or dysplasia is required. The central reader

will also perform a friability assessment (yes, no) for each endoscopy, except for those with an assessed endoscopy subscore of 0, which requires that no friability is present.

Participant eligibility at baseline will be based on the **final reported endoscopic subscore** as determined by the following process:

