- If the local endoscopist and the central reader agree on the endoscopic subscore, the agreed score will be the **final reported endoscopic subscore**.
- If there is a discrepancy between the local endoscopist and the central reader scores, the video endoscopy will be submitted to a second central reader (designated for adjudication) who is blinded to the scores of the local and the first central reader. From the scores of the 3 readers (i.e., local reader, central reader, second central reader designated for adjudication), the score with which 2 readers agree will be reported as the **final reported endoscopic subscore**. If the scores of the 3 readers (ie, local reader, central reader, second central reader designated for adjudication) are all different, then the median score of the 3 scores will be the **final reported endoscopic subscore**.

Further details are provided in the imaging charter.

Unless otherwise specified, the analysis of endpoints that include the Mayo endoscopy subscore will be based on the final reported endoscopic subscore. If the final reported endoscopic score is not available, the corresponding central endoscopy score (central read 1) will be used, if available. If the central endoscopy score (central read 1) is also missing, then the local endoscopy score will be used, if available. If the local endoscopy score is not available, then the endoscopy subscore for the analysis will be left missing.

Mayo Physician's Global Assessment Subscore

The physician's global assessment acknowledges the 3 other Mayo subscores, the patient's recall of abdominal discomfort and general sense of well-being, and other observations, such as physical findings and the patient's performance status.

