Attachment 1: MAYO SCORE

Mayo scoring system for assessment of ulcerative colitis activityStool frequency^a

- 0 = Normal number of stools for this patient
- 1 = 1-2 stools more than normal
- 2 = 3-4 stools more than normal
- 3 = 5 or more stools more than normal

Rectal bleeding^b

- 0 = No blood seen
- 1 = Streaks of blood with stool less than half the time
- 2 = Obvious blood with stool most of the time
- 3 = Blood alone passed

Findings of endoscopy

- 0 = Normal or inactive disease
- 1 = Mild disease (erythema, decreased vascular pattern, mild friability)
- 2 = Moderate disease (marked erythema, absent vascular pattern, friability, erosions)
- 3 = Severe disease (spontaneous bleeding, ulceration)

Physician's global assessment^c

- 0 = Normal
- 1 = Mild disease
- 2 = Moderate disease
- 3 = Severe disease

^a At the screening visit, each person indicates the number of stools he/she passed in a 24-hour period when in remission or before his/her UC diagnosis, thereby serving as his/her own control to establish the degree of abnormality of stool frequency.

^b The daily bleeding score represents the most severe bleeding of the day.

^c The physician's global assessment acknowledges the 3 other criteria, the patient's recall of abdominal discomfort and general sense of well-being, and other observations, such as physical findings and the patient's performance status.

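### The SAP adds a no-friability condition to endoscopic healing under the protocol's name without flagging it, and gives no rule for which friability flag applies after adjudication

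*SAP*

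**What the plan says.** **The definition.** Protocol 3.2.3 lists "Endoscopic healing at Week 12 (Mayo endoscopic subscore of 0 or 1" in brackets as the whole definition, and builds mucosal healing and healing by negative response signature status on it. In SAP 5.5.1.1.3, endoscopic healing "is defined as an endoscopy subscore of 0 or 1 with no friability present on the endoscopy". SAP 5.5.1.1.7 defines mucosal healing through that section, and SAP 5.5 analyses healing by signature status under the same name.

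**The scale.** SAP Attachment 1 grades endoscopy with "1 = Mild disease (erythema, decreased vascular pattern, mild friability" among its levels. Protocol Appendix 8 uses the same wording.

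**The friability read.** SAP 5.3.1.1 says the central reader "will also perform a friability assessment (yes, no) for each endoscopy, except for those with an assessed endoscopy subscore of 0", and adds that a 0 requires friability to be absent.

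**The subscore.** When the local and central reads differ, "the video endoscopy will be submitted to a second central reader (designated for adjudication) who is blinded to the scores" of the other two. Then "the score with which 2 readers agree will be reported as the" final subscore, or the median if all three differ. Endpoints use this final subscore. If it is missing, central read 1 is used. "If the central endoscopy score (central read 1) is also missing, then the local endoscopy score will be used, if available". Further detail is left to the imaging charter.

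**Missing status.** SAP 5.5.3 counts a missing binary endpoint as not achieved.

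**The concern.** Endoscopic improvement is the first-listed secondary objective in Protocol 3.1.2. If the SAP tightens the endpoint that serves it and keeps the name, a reader of the results will take the rate as the protocol's endpoint when it is a stricter one. Elsewhere the SAP does signal such differences. Section 5.2.1 relates its 2-sided 0.2 level to the protocol's 1-sided 0.1, and section 5.5.1.1.4 notes that normalization has been renamed. Nothing comparable accompanies the healing definition.

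The second question is operational. The endpoint now combines a subscore that can be settled by three reads with a yes/no flag for which no adjudication is described. Unless the source of the flag is fixed in advance, two programmers could classify the same participant differently.

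**Working it through.** The plan states no rate, sample size or power for endoscopic healing, so there is no figure to reproduce. The power table in Protocol 9.2 concerns clinical response, which has no friability condition, and is untouched. The check compares definitions and then works through the reading rule.

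**1. Does the added condition change anything?**
- Subscore 0: SAP 5.3.1.1 says 0 already requires no friability. The condition adds nothing here. For the same reason normalization, "Normalization of endoscopic appearance of the mucosa (Mayo endoscopic subscore of 0" in the protocol, is not changed in substance by SAP 5.5.1.1.4.
- Subscore 1: the scale allows mild friability. A participant with final subscore 1 and friability is healed by Protocol 3.2.3 and not healed by SAP 5.5.1.1.3.

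The two definitions therefore differ exactly on friable participants at subscore 1.

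**2. How large could the difference be?** Fall in points = 100 × healing rate × share of healed at subscore 1 × share of those friable. All three inputs are assumptions; the documents give none of them.

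| Protocol-defined healing | Share at subscore 1 | Share of those friable | Fall (points) |
|---|---|---|---|
| 35% | 60% | 10% | 2.1 |
| 50% | 60% | 20% | 6.0 |
| 50% | 75% | 40% | 15.0 |

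**3. Which flag applies after adjudication?** Write a read as (local, central 1, central 2), each 0 to 3. There are 4 × 4 × 4 = 64 patterns. Removing the 4 × 4 = 16 in which local and central 1 agree leaves 48 that go to adjudication. The final subscore is the median of the three, which equals the shared score when two agree.
- 24 of the 48 give a final subscore of 0 or 1.
- In 14 of these 24, central read 1 differs from the final subscore: it is higher in 9 and lower in 5.
- Of the 9, three have a final 0: (0,1,0), (0,2,0), (0,3,0). A friable flag from central 1 would contradict the SAP's own statement about subscore 0.
- The other six have a final 1 with central 1 at 2 or 3: (0,2,1), (0,3,1), (1,2,0), (1,2,1), (1,3,0), (1,3,1).
- In the 5 lower cases central 1 read 0 and the final is 1: (1,0,1), (1,0,2), (1,0,3), (2,0,1), (3,0,1). That reader made no friability assessment.
- In four patterns neither central read equals the final: (1,2,0), (1,3,0), (1,0,2), (1,0,3). A rule that takes the flag from the matching central read would have nothing to take.

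These are counts of patterns, not probabilities.

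**4. Local-only scores.** If both the final score and central read 1 are missing, the local score is used, and no local friability read is described. A local 0 needs none. A local 1 has no stated classification; if it is treated as missing, SAP 5.5.3 makes it a failure.

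**The case against.** The strongest reply is that these are other efficacy endpoints with nominal p-values and no multiplicity control. The primary and major secondary endpoints (SAP 5.3.1 and 5.4.1) carry no friability condition. The same rule applies in every arm, so it does not by construction favour one. Protocol 9.4.1.4 also leaves details of these comparisons to the SAP. All of this stands and limits the importance of the point. It does not license the change, because Protocol 3.2.3 had already defined healing and did not mark it as open.

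Several stronger readings are tempting but unsupported:
- **That an overruled read will deny healing.** The SAP does not say that only central reader 1 records friability, nor that an overruled flag prevails. The adjudicator is also a central reader, and the imaging charter may settle the matter. The documents support only that the SAP itself gives no rule.
- **That the alternative remission definitions are departures too.** Protocol 3.2.2 expressly allows other remission definitions in the SAP, and SAP 5.5.1.1.5 labels them as alternatives.
- **That the protocol defers nothing but remission to the SAP.** It also defers fatigue response (3.2.3) and treatment failures from medication changes (6.5.1). Neither covers healing.
- **That falling back on the local read always produces failure.** A local 0 needs no flag, and the fallback applies only when two other scores are missing.
- **That the healing rate will fall by a known amount.** The range in the working rests wholly on assumed inputs.

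**Conclusion.** The change of definition is plain on the text and rests on no assumption. The SAP's endoscopic healing is stricter than the protocol's, bears the same name, and is not flagged. As written, protocol-defined endoscopic healing, mucosal healing and healing by signature status would not be reported. How far the rates fall depends on how many participants at subscore 1 are friable, which the documents do not say. The 2 to 15 points above illustrate assumed inputs and are not an estimate.

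The second part is narrower: the SAP does not state which friability flag applies to a final subscore of 1 when the first central read is overruled, nor how a local-only subscore of 1 is classified. Whether any participant is affected depends on the charter and on how often reads disagree, neither of which is available. The point deserves correction, but it does not bear on whether the study is declared positive.

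**What to change.** 1. Report endoscopic healing and mucosal healing, including healing by signature status, by the protocol definition (subscore 0 or 1) under the protocol's name. Report the friability-free version alongside under a name of its own, and say in the SAP that it is additional to the protocol.
2. For every endpoint that keeps the friability condition, state in the SAP, consistently with the imaging charter:
   - that a final subscore of 0 counts as no friability;
   - which central read's flag applies to a final subscore of 1, including when neither central read equals the final score and when two central flags differ;
   - how a local-only subscore of 1 is classified, so that every participant in the full analysis set has a status.

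The rule should use reads already recorded. The SAP reports an interim analysis in April 2020 on 126 participants, so many reads were complete by then, and a new field on the adjudication form would not recover them without re-reading videos. On this basis the cost is SAP wording and one extra table row per affected endpoint.

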5.5.1.1.5. Clinical remission by alternative definitions

Clinical Remission (UNIFI definition) is defined as an absolute stool number ≤ 3 , a rectal bleeding subscore of 0, and an endoscopy subscore of 0 or 1 with no friability present on the endoscopy.

Clinical Remission (Health Authority definition 1) is defined as a stool frequency subscore of 0 or 1, a rectal bleeding subscore of 0, and an endoscopy subscore of 0 or 1 with no friability present on the endoscopy, where the stool frequency subscore has not increased from baseline.

Clinical Remission (Health Authority definition 2) is defined as a stool frequency subscore of 0, a rectal bleeding subscore of 0, and an endoscopy subscore of 0 or 1 with no friability present on the endoscopy.

5.5.1.1.6. Histologic healing

Histologic healing is defined as 0 - $< 5\%$ neutrophils in epithelium and no crypt destruction, and no erosion, ulceration, or granulation tissue according to the Geboes grading system³ ([Attachment 3](#)).

5.5.1.1.7. Mucosal healing

Mucosal healing is a combination of histologic healing (Section 5.5.1.1.6) and endoscopic healing (Section 5.5.1.1.3).

5.5.1.1.8. Histologic remission

Histologic remission is defined as absence of neutrophils from the mucosa (both lamina propria and epithelium), no crypt destruction, and no erosions, ulcerations or granulation tissue according to the Geboes grading system³ (Attachment 3).

5.5.1.1.9. Histologic-endoscopic mucosal healing

Histologic-endoscopic mucosal healing is a combination of histologic remission (Section 5.5.1.1.8) and endoscopic healing (Section 5.5.1.1.3).

5.5.1.1.10. Deep histologic-endoscopic mucosal healing

Deep histologic-endoscopic mucosal healing is a combination of histologic remission (Section 5.5.1.1.8) and endoscopic normalization (Section 5.5.1.1.4).

5.5.1.1.11. Geboes Scores

The **Geboes total score**, a continuous histology score, is calculated as the sum of all Geboes Grades (Attachment 3) and may take on values from 0 to 22.

The **Geboes high activity subscore**, a continuous histology score, is calculated as the sum of Geboes Grades 3, 4, and 5 and may take on values from 0 to 10.

The **Geboes low activity subscore**, a continuous histology score, is calculated as the sum of Geboes Grades 0, 1, 2A and 2B and may take on values from 0 to 12.

5.5.1.1.12. Roberts Histologic Index (RHI)-based histologic remission

RHI-based histologic remission is defined as $RHI \leq 3$ with sub-scores of 0 for lamina propria neutrophils and neutrophils in the epithelium according to the Roberts Histologic Index⁷ (Attachment 4).

5.5.1.1.13. Nancy Histologic Index (NHI)-based histologic remission

NHI-based histologic remission is defined as $NHI \leq 1$ according to the Nancy Histologic Index⁶ (Attachment 5).

5.5.1.1.14. Ulcerative Colitis Endoscopic Index of Severity (UCEIS)

The UCEIS (Attachment 6) is an index that provides an overall assessment of endoscopic severity of UC, based on mucosal vascular pattern, bleeding, and ulceration¹². The score ranges from 3 to 11, with a higher score indicating more severe disease by endoscopy. The UCEIS score will be assessed only by the central video readers for all endoscopies.

5.5.1.2. Inflammatory Biomarkers

5.5.1.2.1. C-Reactive Protein

C-reactive protein (CRP) has been demonstrated to be useful as a marker of inflammation in participants with IBD. In subjects with UC, elevated CRP has been associated with more severe clinical activity, an elevated sedimentation rate, and active disease as detected by colonoscopy^{11,15}.

5.5.1.2.2. Fecal Calprotectin

Fecal calprotectin has been demonstrated to be a sensitive and specific marker in identifying intestinal inflammation and response to treatment in participants with IBD, especially in UC¹.

Assays for fecal calprotectin concentration will be performed by the central laboratory using a validated method. Additional tests may also be performed on the stool samples for additional markers that are related to intestinal inflammation and treatment response such as the microbiome.

5.5.1.3. HRQoL Endpoints

5.5.1.3.1. Inflammatory Bowel Disease Questionnaire (IBDQ)

The **IBDQ**⁴ is a validated, 32-item, self-reported questionnaire for participants with IBD that will be used to evaluate the disease-specific HRQOL across 4 dimensional scores: bowel symptoms (loose stools, abdominal pain), systemic function (fatigue, altered sleep pattern), social function (work attendance, need to cancel social events), and emotional function (anger, depression, irritability). Scores range from 32 to 224, with higher scores indicating better outcomes.

The individual IBDQ dimensions will be calculated when no more than 1 item is missing in the dimension. If an item is missing, it will be estimated using the average value across the non-missing items. If any of the 4 dimensions of the IBDQ cannot be calculated, then the total IBDQ score cannot be calculated and will be missing for that visit.

5.5.1.3.2. PROMIS-29

The **PROMIS-29** is a validated general health profile instrument that is not disease-specific. It is a collection of short forms containing 4 items for each of 7 domains (depression, anxiety, physical function, pain interference, fatigue, sleep disturbance, and ability to participate in social roles and activities). PROMIS-29 also includes an overall average pain intensity 0-10 numeric rating scale. Norm-based scores have been calculated for each domain on the PROMIS measures, with a score of 50 representing the mean or average of the reference population. On symptom-oriented domains of PROMIS-29 (anxiety, depression, fatigue, pain interference, and sleep disturbance), higher scores represent worse symptomatology. On the function-oriented domains (physical functioning and social role), higher scores represent better functioning.

5.5.1.3.3. PROMIS Fatigue 7-items Short Form

The **PROMIS Fatigue Short Form 7a** contains 7 items evaluating fatigue-related symptoms (ie, tiredness, exhaustion, mental tiredness, and lack of energy) and associated impacts on daily activities (ie, activity limitations related to work, self-care, and exercise). PROMIS Fatigue Short

Form 7a has a recall period of past 7 days. Compared to the fatigue scale of PROMIS-29, PROMIS Fatigue Short Form 7a provides additional information to evaluate severity of fatigue.

Fatigue response is defined as a ≥ 5 -point improvement in the PROMIS Fatigue Short Form 7a.

